12.8. Definitions for Response Evaluation – RECIST 1.1

12.8.1. Objective Response Rate

The objective response rate is the proportion of all subjects with confirmed PR or CR according to RECIST 1.1, from the start of treatment until disease progression/recurrence (taking as reference for progressive disease the smallest measurements recorded since the start of treatment).

12.8.2. Clinical Benefit Rate

The Clinical Benefit rate is the proportion of all subjects with stable disease (SD) at ≥ 6 months from cycle 1 day 1, or partial response (PR), or complete response (CR) according to RECIST 1.1, from the start of treatment until disease progression/recurrence (taking as reference for progressive disease the smallest measurements recorded since the start of treatment).

12.8.3. Progression Free Survival

A measurement from study treatment day 1 until the criteria for disease progression is met as defined by RECIST 1.1 or death occurs. Subjects who have not progressed will be right-censored at the date of the last disease evaluation.

12.8.4. Overall Survival

Overall survival is defined by the date of study treatment day 1 to date of death from any cause.

12.8.5. Duration of Response

Duration of overall response—the period measured from the time that measurement criteria are met for complete or partial response (whichever status is recorded first) until the date that recurrent or progressive disease is objectively documented (taking as reference for progressive disease the smallest measurements recorded since treatment started).

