2. OBJECTIVES AND OUTCOME MEASURES

2.1. Primary

Objective	Brief Description/Justification of Outcome Measure	Outcome Measured By	Time Frame
Evaluate ORR in patients receiving NKTR-214 in combination with palliative radiation, and pembrolizumab.	Response to anti-PD-1 therapy can be quite durable in patients with metastatic or recurrent HNSCC (~ 22 months); however, low ORR (~ 20 %) limits therapeutic benefit in this population as a whole. Improving ORR could result in a dramatic impact on survival of patients with metastatic or recurrent HNSCC.	ORR will include confirmed CR + confirmed PR and will be determined as per RECIST1.1. Progression of any radiated tumors will be considered in this evaluation but response of radiated tumor(s) will not be considered as evidence of response for the purpose of this study.	
 Pre-treatment standard-of-care imaging Standard-of-care imaging 3 to 6 months after Cycle 1

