2.2. Secondary

Objective	Brief Description/Justification of Outcome Measure	Outcome Measured By	Time Frame
Evaluate the safety of NKTR-214 in combination with anti-PD-1 therapy and palliative radiation.	Grade 3 or grade 4 adverse event except those listed in 8.3.2 are anticipated to occur in < 25 % of patients based on the previous rate of 11 % with PD-1 inhibition and radiation. The safety of this combination must be established prior to evaluation of efficacy.	Toxicities \geq Grade 3 will be defined by the NCI Common Terminology Criteria for Adverse Events (CTCAE) v5. Toxicities not determined to be "unrelated" to treatment, will be considered treatment-related (including those that are unlikely, possibly, probably, or definitely related).	
 Study screening Cycle 1, day 1, 8 Cycle 2, day 1, 8 Cycle 3+, day 1 Every 4 months once off study without progression for 5 years, Every 6 months once off study with progression for 3 years

Objective	Brief Description/ Justification of Outcome Measure	Outcome Measured By	Time Frame
Determine CB, PFS, duration of response, and OS after treatment with NKTR-214, anti- PD-1, and palliative radiation.	PFS, OS, CB, and duration of response were chosen as efficacy outcomes based on prior immunotherapy trials. Duration of response is particularly important, as more durable responses are expected with immunotherapy.	
 CB will include confirmed complete response (CR) + confirmed partial response (PR) + stable disease at \geq 6 months (SD) and will be determined as per RECIST1.1. PFS is defined as the time from D1 of treatment until the criteria for disease progression is met as defined by RECIST1.1 or death as a result of any cause. OS is defined as time from D1 of treatment until death as a result of any cause. Duration of response is the period measured from the time that measurement criteria are met for complete or partial response (whichever status is recorded first) until the date that recurrent or progressive disease is objectively documented. 	
 D1 of treatment Standard-of-care imaging follow-up \sim3 and 6 months after Cycle 1 Time of disease progression Death

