11.2. Sample Size Considerations

This study will enroll 24 participants to test the hypothesis that the combination of NKTR-214 with palliative radiation and anti-PD-1 therapy results in an ORR $\geq 44\%$. Under the null hypothesis for ORR ≤ 0.22 , based on one-sided one sample proportion test with type I error of 0.1, the expected power levels to detect alternative ORRs of 0.35, 0.4, and 0.45 are 55 %, 74 %, 87 % respectively. The null hypothesis will be rejected and superiority concluded if 8 or more responses are observed in 24 participants. This design yields a type I error rate of .04 and power of .8 when the true response rate is 44 %.

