11.3.2. Analysis Plans for Secondary Objectives

Treatment-related AE will be reported in tabular format, and AE rates, including the proportion of participants experiencing Grade 3+ treatment-related toxicities, will be reported with the 95 % CI.

PFS will be analyzed using the Kaplan-Meier method, and median PFS will be computed with the associated 95 % CI. Subjects who have not progressed and are still alive will be right-censored at the date of the last disease evaluation. Kaplan-Meier curves will be plotted.

OS will be analyzed using the Kaplan-Meier method, and median OS will be computed with the associated 95 % CI. Subjects who have not died will be right-censored at the date of the last follow-up, and Kaplan-Meier curves will be plotted.

Clinical benefit rate (defined as CR + PR + SD at \geq 6 months) will be reported via waterfall plot, and the 95 % CI for the clinical benefit rate will be computed.

Duration of response, duration of overall complete response and time to progression will be evaluated using the Kaplan-Meier method. Medians will be computed with the associated 95 % CI, and Kaplan-Meier curves will be plotted.

Patient-reported health-related quality of life will be evaluated using summary statistics and generalized linear mixed-effects models for measurements over time.

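### Duration of response has no death event, so responders who die without documented progression would by implication be censored, which can lengthen the reported duration but never shorten it

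*Combined protocol and SAP*

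**What the plan says.** Duration of response is a secondary efficacy endpoint, defined in the Protocol Summary, the section 2.2 table and section 12.8.5. In all three places it starts when the criteria for CR or PR are first met and lasts "until the date that recurrent or progressive disease is objectively documented". None of the three lists death as an end of response.

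The analysis is in section 11.3.2: "Duration of response, duration of overall complete response and time to progression will be evaluated using the Kaplan-Meier method", with medians and 95% confidence intervals. That section gives censoring rules for PFS and OS. It gives none for duration of response and names no competing-risk method.

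PFS is handled differently. Section 12.8.3 measures it "until the criteria for disease progression is met as defined by RECIST 1.1 or death occurs", and section 11.3.2 says of PFS: "Subjects who have not progressed and are still alive will be right-censored at the date of the last disease evaluation". Nothing extends that rule to duration of response.

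The protocol gives the endpoint weight. Section 2.2 states: "Duration of response is particularly important, as more durable responses are expected with immunotherapy".

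**The concern.** Kaplan-Meier needs each responder to have either an event or a censoring time. If only documented progression is an event, a responder who dies without it can only be censored. The curve then treats that patient as someone whose response might have continued beyond death. The same death counts against the treatment in PFS but not in duration of response, so the two endpoints can tell different stories about the same patients.

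The protocol's own schedule makes such deaths plausible:

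- On-treatment imaging is every fourth 21-day cycle from cycle 3 (section 6.5.1; Appendix A, footnote 12).
- Imaging at treatment discontinuation is left to the investigator (same footnote).
- After stopping without progression, follow-up is every 4 months ± 30 days (Appendix A, footnote 5).
- Section 12.7 foresees patients who stop for symptomatic deterioration without objective progression.

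Some of these deaths may reflect progression that no scan recorded, in which case the censoring would be informative. Few responders are expected, so one or two reclassified deaths can change the median.

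**Working it through.** The documents state no target, event count or power for duration of response, so there is no planned figure to reproduce. The check covers how the rules treat one death, the direction of the effect, and its possible size.

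**1. One death under each rule.** Take a responder who dies with no documented progression.

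| Endpoint | End events in the plan | This death is |
|---|---|---|
| PFS (12.8.3, 11.3.2) | progression or death | an event |
| Duration of response (Summary, 2.2, 12.8.5) | documented recurrence or progression | not an event, so censored by implication |

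**2. Inputs from the documents.**
- Scan interval on treatment: 4 × 21 days = 84 days = 12 weeks.
- Sample size: 24 (section 11.2).
- Expected responders: 24 × 0.44 = 10.56 at the target rate; 24 × 0.22 = 5.28 at the null rate.
- Share q of ended responses that are deaths without documented progression: not given. Assumed range 10% to 30%.

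**3. Direction.** At each event time the Kaplan-Meier curve is multiplied by (1 − 1/number at risk). Changing a death from event to censored removes one such factor and leaves the numbers at risk at later times unchanged. The curve can stay the same or rise, but cannot fall.

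A made-up example shows this. Eleven responses last 3, 5, 6, 8, 9, 12, 14, 18, 20, 24 and 30 months; the first seven end and the last four are censored.
- All seven counted as events: the curve is 6/11 = 0.545 after month 9 and 5/11 = 0.455 after month 12. Median 12 months.
- Endings at months 5 and 9 are deaths and are censored: 10/11 × 8/9 × 7/8 × 5/6 = 0.589 after month 12, then × 4/5 = 0.471 after month 14. Median 14 months.

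**4. Size, as an illustration.** Let progression and death without documented progression have constant independent hazards a and b, so q = b/(a + b).
- Median to progression or death: ln 2/(a + b).
- Median with deaths censored: ln 2/a.
- Ratio: (a + b)/a = 1/(1 − q).

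| Assumed q | 1/(1 − q) | Inflation of the median |
|---|---|---|
| 0% | 1.000 | none |
| 10% | 1/0.9 = 1.111 | 11% |
| 20% | 1/0.8 = 1.250 | 25% |
| 30% | 1/0.7 = 1.429 | 43% |

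**5. Small samples.** A simulation used 5, 8 and 11 responders, q of 10%, 20% and 30%, censoring uniform over 9 to 36 months and 8,000 runs per setting. The median to progression or death was set at 22 months purely as a time scale. The deaths-censored median was never below the progression-or-death median. With 11 responders it was higher in 17%, 33% and 45% of runs at q = 10%, 20% and 30%; in the other runs it did not change. At q = 30%, the share of runs with the median not reached rose from 28% to 54%.

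**The case against.** **Censoring of deaths is an inference.** This is correct. No section says that responders who die are censored, or on what date. It follows from a progression-only end event combined with plain Kaplan-Meier. If the sponsor intends something else, the text still needs to say so.

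**Such deaths may be uncommon.** A reader might take the 6 to 12 month median survival in section 1.1.1 to mean that death before a progression scan is likely. The documents do not support that. The figure describes recurrent or metastatic patients as a whole, while duration of response is measured in responders, who should live longer. The protocol also allows imaging whenever clinically indicated (7.1.12), asks for efforts to document progression after treatment stops (12.7), and follows patients without progression for 5 years (8.2.2). These provisions reduce undocumented progression without excluding it, so plausible is as far as the documents go.

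**Duration is not always overstated.** There is no effect if no responder dies without documented progression, and a death late in the curve need not move the median.

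**The 22 months in section 2.1 cannot be converted.** It is tempting to scale that background figure up or down by 1/(1 − q). The documents do not say whether it counts death, so neither conversion is justified.

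**The share q does not give a number of deaths.** It is a share of ended responses, not of all responders, and the number that will have ended by the analysis is not stated. Multiplying 20% to 30% by 10 or 11 responders would be wrong.

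**A progression-only measure may be intended.** Possibly, but section 11.3.2 already lists time to progression separately, so that purpose is served. It is also true that no test or decision rule uses duration of response, and that the deaths still count in PFS and OS. This limits the consequence but does not remove the defect.

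**Conclusion.** The point holds as a defect of definition with a known direction. Followed as written, the plan leaves a responder who dies without documented progression with no event, and plain Kaplan-Meier then censors that patient. Relative to a progression-or-death definition, the reported duration can be the same or longer, never shorter.

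The size is not determinable from the documents. The 11%, 25% and 43% figures rest on an assumed q and on constant independent hazards. If deaths are linked to unrecorded progression, independence fails, so the figures show scale only. At q = 0 there is no effect.

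The primary endpoint is untouched. The change should nevertheless be made before analysis, because the protocol singles this endpoint out and the correction is easy.

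**What to change.** Amend the Protocol Summary, the section 2.2 table, section 11.3.2 and section 12.8.5 to say:

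- Duration of response is the time from the first documented CR or PR (later confirmed) to documented progression or death from any cause, whichever comes first.
- Responders alive and progression-free are censored at their last disease evaluation.
- Duration of complete response follows the same event and censoring rule.

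Time to progression can stay in section 11.3.2 as the progression-only measure, labelled as such.

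The cost is a wording change. Deaths are already collected for PFS and OS, so no new data are needed. The one downside is that the reported duration may be shorter than under the present definition.

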13. SOURCE DOCUMENTS AND ACCESS TO SOURCE DATA/DOCUMENTS

Study staff will maintain appropriate medical and research records for this study, in compliance with ICH E6, Section 4.9 and regulatory and institutional requirements for the protection of confidentiality of participants. Study staff will permit authorized representatives of regulatory agencies to examine (and when required by applicable law, to copy) research records for the purposes of quality assurance reviews, audits, and evaluation of the study safety, progress, and data validity.

Source documents will include all records within the HealthLink Electronic Medical Records system such as hospital records, clinical and office charts, laboratory notes, memoranda, pharmacy dispensing records, copies or transcriptions certified after verification as being accurate and complete, photographs or digital photo files, x-rays, and subject files and records kept at the pharmacy, at the laboratories, and medico-technical departments involved in the clinical trial. In addition, protocol specific forms will be designed which require treating physician signature to serve as source documents. This may include forms such as toxicity forms with grading and attribution and tumor measurement forms.

14. ETHICS/PROTECTION OF HUMAN SUBJECTS

14.1. Ethical Standard

The investigator will ensure that this study is conducted in full conformity with the principles set forth in The Belmont Report: Ethical Principles and Guidelines for the Protection of Human Subjects of Research, as drafted by the US National Commission for the Protection of Human Subjects of Biomedical and Behavioral Research (April 18, 1979) and codified in 45 CFR Part 46 and/or the ICH E6.

14.2. Institutional Review Board (IRB)

The final study protocol and the final version of the informed consent form must be approved in writing by the University of Wisconsin Health Sciences IRB.

The site investigator is responsible for informing the IRB of any amendment to the protocol in accordance with local requirements. In addition, the IRB must approve all advertising used to recruit subjects for the study. The protocol must be re-approved by the IRB as local regulations require.

Progress reports and notifications of AEs will be provided to the IRB according to local regulations and guidelines.

14.3. Informed Consent Process

The subject's signed and dated informed consent must be obtained before conducting any procedure specifically for the study. The site investigator must store the original, signed informed consent form. A copy of the signed informed consent form must be given to the subject. A consent form describing in detail the study procedures and risks will be given to the participant. Consent forms will be IRB-approved, and the participant is required to read and review the document or have the document read to him or her.

The investigator or designee will explain the research study to the participant and answer any questions that may arise. The participant will sign the informed consent document prior to any research-only assessments or procedures. Participants will be given the opportunity to discuss the study with their surrogates or think about it prior to agreeing to participate. They may withdraw consent at any time throughout the course of the study. The rights and welfare of the participants will be protected by emphasizing to them that the quality of their clinical care will not be adversely affected if they decline to participate in this study.

The consent process will be documented in the clinical or research record.

14.4. Exclusion of Children (Special Populations)

Adults of any gender or racial/ethnic group may participate. Since children do not make up a significant portion of the subjects with recurrent metastatic head and neck squamous cell carcinoma, children are excluded from this study.

14.5. Subject Confidentiality

Subject confidentiality is strictly held in trust by the investigators, study staff, and the study sponsor(s) and their agents. This confidentiality is extended to cover testing of biological samples and genetic tests in addition to any study information relating to participants.

The study protocol, documentation, data, and all other information generated will be held in strict confidence. No information concerning the study or the data will be released to any unauthorized third party without prior written approval of the study sponsor.

The study shall be conducted in full compliance with (i) all applicable laws, regulations, and guidance of Regulatory Authorities relating to human clinical research of the type described in the Protocol, including the United States Federal Food, Drug and Cosmetic Act ("FDC Act") and the relevant provisions of Title 21 of the United States Code of Federal Regulations; (ii) generally accepted standards of Good Clinical Practice ("GCP"), including ICH E6 Good Clinical Practice: Consolidated Guidance (April 1996) as adopted by the FDA; and (iii) all applicable laws relating to the collection, use, storage and disclosure of individually-identifiable patient medical information, records and data, including but not limited to the Health Insurance Portability and Accountability Act of 1996 as amended by the Health Information Technology for Economic and Clinical Health Act of 2009 and similar state, local and foreign laws (collectively "Privacy and Security Regulations").

Regulatory Authorities will have access to any and all of the following as may be required by applicable law and regulations or guidances of Regulatory Authorities: (i) the Principal Investigator, any other Investigator, or other personnel involved with the Study; (ii) Study facilities; and (iii) books, accounts, Study Drug records, patient records, case report forms, source data (as that term is defined and used in ICH E6 Good Clinical Practice: Consolidated Guidance (April 1996)), and other records, documents, materials and sources of information related to the Study ("Records").

AEs will be reported to Regulatory Authorities promptly in compliance with applicable law. In addition, any Serious Adverse Event ("SAE") will be reported to Nektar within 24 hours from the time it is determined by study personnel that such an event or reaction has occurred, or immediately if the event or reaction is fatal or life-threatening.

14.5.1. Certificate of Confidentiality

To further protect the privacy of study participants, the Secretary of Health and Human Services (HHS), has issued a Certificate of Confidentiality (CoC) to all researchers engaged in biomedical, behavioral, clinical, or other human subjects research funded wholly or in part by the federal government. Recipients of NIH funding for human subjects research are required to protect identifiable research information from forced disclosure per the terms of the NIH Policy (<https://humansubjects.nih.gov/coc/index>). As set forth in [45 CFR Part 75.303\(a\)](#) and [NIH GPS Chapter 8.3](#), recipients conducting NIH-supported research covered by this Policy are required to establish and maintain effective internal controls (e.g., policies and procedures) that provide reasonable assurance that the award is managed in compliance with Federal statutes, regulations, and the terms and conditions of award. It is the NIH policy that investigators and others who have access to research records will not disclose identifying information except when the participant consents or in certain instances when federal, state, or local law or regulation requires disclosure. NIH expects investigators to inform research participants of the protections and the limits to protections provided by a Certificate issued by this Policy.

14.5.2. NIH Data Sharing Policies

For this study, the correlative objectives are funded in part, through the NIH. As described in section 17, it is NIH policy that the results and accomplishments of the activities that it funds should be made available to the public (see <https://grants.nih.gov/policy/sharing.htm>). PIs and funding recipient institutions will ensure that all mechanisms used to share data include proper

plans and safeguards to protect the rights and privacy of individuals who participate in NIH-sponsored research. This will apply to the results of the correlative outcomes analysis.

14.6. Future Use of Stored Specimens and Other Identifiable Data

Subject consent will be obtained to bank any leftover samples that were collected for study-specific correlative research. The UW H&N SPORE Pathology Core facility and/or the [name] lab will manage the banked samples. All patient health information with the sole exception of sample date will be removed. The sample date will be available to the study team only to facilitate database structure. Any samples provided to collaborators; however, will be stripped of all PHI, including the date. Instead, samples will be coded with research sample ID and time point description.

